**Table 3-1 Study VX19-445-115: Part A Treatment Period and Safety Follow-up Visit**

Event/Assessment a	Treatment Period Part A					Part A ETT Visit/ Departing Visit b	Part A Safety Follow-up Visit (28 ± 7 Days After Last Dose) c	Comments
	Day 1/ Returning Visit d	Day 15 (± 3 Days)	Weeks 4, 12, 24, 36 (± 5 Days)	Weeks 8, 16, 20, 28, 32, 40, 44 (± 5 Days)	Week 48 (± 5 Days) e			
Ophthalmologic examination					X	X		Subjects <18 years of age on the date of informed consent in a parent study and have completed at least 12 weeks of study drug treatment since their last ophthalmologic examination will have an ophthalmologic examination at the Part A Week 48 Visit or the Part A ETT Visit/ Departing Visit, whichever comes first. See Section 11.2.7 for acceptable assessment windows.
Complete physical examination (PE)	X				X	X		Symptom-directed PEs may be performed at any time if deemed necessary by the investigator (Section 11.2.3)
Pregnancy test	Urine		Urine	Urine	Serum	Serum	Serum	For all female subjects, at telephone contacts, a urine pregnancy test will be performed with a home kit provided by the study site. Results of the home pregnancy test will be reported to the site by telephone (Section 11.2.2).
Standard 12-lead ECG	X	X	Weeks 12, 24		X	X	X	Performed after subject has been at rest for at least 5 minutes (Sections 11.2.3, 11.2.5, and 11.2.6)
Vital signs	X	X	X		X	X	X	
Pulse oximetry	X	X	X		X	X	X	
Urinalysis	X				X	X	X	Section 11.2.2
Hematology	X	X	X		X	X	X	
Coagulation	X		Week 24		X	X	X	
Serum chemistry	X	X	X		X	X	X	
Study drug count	X	X	X		X	X		

Event/Assessment a	Treatment Period Part A					Part A ETT Visit/ Departing Visit b	Part A Safety Follow-up Visit (28 ± 7 Days After Last Dose) c	Comments
	Day 1/ Returning Visit d	Day 15 (± 3 Days)	Weeks 4, 12, 24, 36 (± 5 Days)	Weeks 8, 16, 20, 28, 32, 40, 44 (± 5 Days)	Week 48 (± 5 Days) e			
Study drug dosing	Day 1 through evening before Part A Week 48 Visit							Subjects on study drug interruption from a parent study or another qualified Vertex study may NOT begin dosing until they meet the resumption criteria in Section 9.8. The last dose of Part A should be taken on the evening before the Week 48 Visit. Refer to Section 9.6.1 for study drug administration details.

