### 3.2 Part B

Event/Assessment a	Treatment Period Part B				Part B ETT Visit/ Departing Visit b	Part B Safety Follow-up Visit (28 ± 7 Days After Last Dose) c	Comments
	Day 1/ Returning Visit d	Weeks 12, 24, 36, 48, 60, 72, 84 (± 5 Days)	Weeks 4, 8, 16, 20, 28, 32, 40, 44, 52, 56, 64, 68, 76, 80, 88, 92 (± 5 Days)	Week 96 (± 5 Days)			
Clinic visit	X	X		X	X	X	
Telephone contact			X				Results of a home urine pregnancy test will be reported to the site by telephone (Section 11.2.2)
Part B ICF and assent (when applicable)	X						ICF and assent are not required for Returning Visit
Inclusion and exclusion criteria confirmation	X						Section 8
Height and weight	X	X		X		X	Measured with shoes off. For subjects whose date of informed consent occurs after their 21 st birthday, height will not be collected (Section 11.2.4).

a All assessments should be performed before study drug dosing, unless noted otherwise.

b If the subject prematurely discontinues study drug treatment, an ETT Visit should be scheduled as soon as possible after the decision to discontinue treatment (Section 9.1.3). If the subject prematurely discontinues treatment to participate in another qualified Vertex study, the Departing Visit should be completed before or on the same day as the visit at which they receive the first dose of study drug in the Run-in Period of the other qualified Vertex study. The Safety Follow-up Visit will not be required if the subject enrolls in the other qualified Vertex study within 28 days of the last dose of study drug in this study.

c The Safety Follow-up Visit is required for all subjects, unless otherwise specified. For subjects who complete an ETT Visit 3 weeks or later following the last dose of study drug, the ETT Visit will replace the Safety Follow-up Visit (Section 9.1.2).

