Urinalysis	X			X	X	X	
Hematology	X	X		X	X	X	
Coagulation	X	Week 48		X	X	X	
Serum chemistry	X	X		X	X	X	
Study drug count	X	X		X	X		

Table 3-2 Study VX19-445-115: Part B Treatment Period and Safety Follow-up Visit							
Event/Assessmenta	Treatment Period Part B				Part B ETT Visit/ Departing Visitb	Part B Safety Follow-up Visit (28 ± 7 Days After Last Dose)c	Comments
	Day 1/ Returning Visitd	Weeks 12, 24, 36, 48, 60, 72, 84 (± 5 Days)	Weeks 4, 8, 16, 20, 28, 32, 40, 44, 52, 56, 64, 68, 76, 80, 88, 92 (± 5 Days)	Week 96 (± 5 Days)			
Study drug dosing	Day 1 through evening before Part B Week 96 Visit						Subjects on study drug interruption from Part A or another qualified Vertex study may NOT begin dosing in Part B until they meet the resumption criteria in Section 9.8. The first dose of Part B will be given at the Day 1 Visit. Refer to Section 9.6.1 for study drug administration details.
Medications review	Continuous from signing of the Part B ICF through completion of study participation						Completion of study participation is defined in Section 9.1.5.
Treatments and procedures review	Continuous from signing of the Part B ICF through completion of study participation						
AEs and SAEs	Continuous from signing of the Part B ICF through completion of study participation						

AE: adverse event; ETT: early termination of treatment; ICF: informed consent form; PE: physical examination; SAE: serious adverse event

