#### **9.1.2 Safety Follow-up**

The Safety Follow-up Visit is scheduled to occur 28 ( $\pm$  7) days after the last dose of study drug in Parts A and B. The Safety Follow-up Visit assessments are listed in Table 3-1 and Table 3-2, respectively.

The Safety Follow-up Visit is required for all subjects. However, subjects in Parts A and B who transition within 28 days of the last dose of study drug to either:

- a commercially available Vertex CFTR modulator regimen
- managed access program-supplied Vertex CFTR modulator regimen
- or, to another Part of the current study or another qualified Vertex study

will complete the respective Part A Week 48 or Part B Week 96 Visit. If the transition occurs before the Part A Week 48 Visit or Part B Week 96 Visit, then subjects will complete the Early Termination of Treatment (ETT) Visit. In these cases, the Part A Week 48/Part B Week 96 Visit or the ETT Visit, whichever is applicable, will replace the Safety Follow-up Visit.

For subjects who complete an ETT Visit 3 weeks or later following the last dose of study drug, the ETT Visit will replace the Safety Follow-up Visit (Section 9.1.3).

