### **9.1.3 Early Termination of Treatment**

#### **Departing Visit**

If a subject enrolls in another qualified Vertex study, the Departing Visit should be completed before or on the same day as the visit at which they receive the first dose of study drug in the Run-in Period of the other qualified Vertex study. If completed on the same day, the Schedule of Assessments in the other qualified Vertex study should be followed and study assessments in this study that were specified to be performed in the other qualified Vertex study do not have to be repeated. If the subject does not resume participation in this study, they will not be required to complete a separate ETT visit.

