#### **ETT Visit**

If a subject prematurely discontinues study drug treatment for any reason other than to enroll in another qualified Vertex study, an ETT Visit should be scheduled as soon as possible after the decision to discontinue treatment.

If the ETT Visit occurs 3 weeks or later following the last dose of study drug, then the ETT Visit will replace the Safety Follow-up Visit, and a separate Safety Follow-up Visit will not be required.

If a subject withdraws from the study and also withdraws consent or assent, no further assessments will be performed. Vertex may retain and continue to use any data and samples collected before such withdrawal of consent or assent.

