1. If no numerical measurement is available within a visit window, the measurement will be considered missing for the visit.
2. If there is more than 1 numerical measurement available within a visit window, use the following rules:
 - i. The measurement closest to the target day will be used; or
 - ii. If there are multiple measurements with the same closest distance from the target day, the latest measurement will be used. For multiple measurements on the same day, unscheduled measurements will be treated as later than scheduled measurement.

³ For measurement collected on the date of first dose of study drug in Treatment Period, if it cannot be determined whether the measurement is before or after the first dose:

- a. Scheduled measurement will be treated as pre-dose observation.
- b. Unscheduled measurement will be treated as post-dose observation.

⁴ For safety Assessment, Safety Follow-up analysis visit will be based on nominal Safety Follow-up visit. If a subject doesn't have a nominal Safety Follow-up visit but has an ETT visit with study day >351 in the corresponding part, then the ETT visit will be mapped into Safety Follow-up analysis visit.

Derived Variables:

1. Age (in years) at first dose date and post-baseline visit (for listing, if applicable):
 - Obtain the age at informed consent in “yy, mm” format (e.g., 24 years, 6 months) in parent study from the Vital Signs (VS) page at the Screening Visit in parent study, and add 0.5 month to convert to days.
 - Obtain the informed consent date in parent study.

Table 12.1 Analysis Visit Windows Safety Assessments			
Panel B: Analysis Visit Windows for Part B			
Assessment	Visit¹	Target Study Day	Analysis Visit Window (in study days)^{2, 3, 4}
			
Then age (in years) at first dose = [(first dose date – informed consent date in parent study) in days + age at informed consent (in days) in parent study]/365.25.

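### SAP Table 12-1 footnote 4 applies the Part A cut-off (study day >351) to Part B, so Part B ETT visits on days 352-687 are sent to Safety Follow-up although they lie inside a Part B week window

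*SAP*

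**What the plan says.** SAP Section 12.1, Table 12-1, has a Panel A for Part A and a Panel B for Part B. Footnote 4 is attached to the window column of both. It bases the Safety Follow-up analysis visit on the nominal visit and adds a fallback for subjects in whom that visit is missing: if such a subject "has an ETT visit with study day >351 in the corresponding part, then the ETT visit will be mapped into Safety Follow-up analysis visit". No other cut-off for Part B appears in the SAP.

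Footnote 2 applies the windows to scheduled and unscheduled visits alike and makes no exception for ETT visits.

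Protocol Section 9.1.2 describes how a subject can have an ETT visit and no Safety Follow-up visit. It covers subjects who move, within 28 days of the last dose, to commercial or managed-access supply or to another study. "If the transition occurs before the Part A Week 48 Visit or Part B Week 96 Visit", the subject completes an ETT visit. The final treatment visit "or the ETT Visit, whichever is applicable, will replace the Safety Follow-up Visit". Under Sections 9.1.2 and 9.1.3, an ETT visit 3 weeks or more after the last dose also replaces Safety Follow-up.

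**The concern.** The cut-off should mark the point after which no week row remains to receive an ETT value. Day 351 does that in Part A. In Part B it is an arbitrary day inside the Week 48 window, and nearly half of the windowed period lies beyond it. The words about the corresponding part settle which part's study day is counted; they do not change the number.

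SAP Section 9.2.3 repeats the Part A safety analyses for Part B, including the by-visit summaries of laboratory values, ECGs and vital signs (Sections 9.1.3.2 to 9.1.3.4). A Part B value taken at or near a week target, possibly soon after the last dose, would leave that week's row and appear as follow-up. The same kind of visit inside a Part A window keeps its week row. The two parts would then follow different rules, with no reason given.

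**Working it through.** **Reproducing the cut-off.** Target day = 7 × week + 1, and the last window ends 14 days after its target.

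- Part A Week 48: 7 × 48 + 1 = 337; 337 + 14 = 351. This is the footnote's number and the end of every Week 48 window in Panel A.
- Part B Week 96: 7 × 96 + 1 = 673; 673 + 14 = 687. This is the end of every Week 96 window in Panel B.

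Panel B counts from Part B Day 1: its Week 96 target is 673. Counted from Part A Day 1 it would be 7 × 144 + 1 = 1009.

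**Days above 351 that lie inside a week window.** Part A has none for any assessment. Part B:

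| Assessment | Window | Days caught | Count |
|---|---|---|---|
| Vital signs, hematology, chemistry | Week 48 (295, 379] | 352-379 | 28 of 84 |
| | Week 60 (379, 463] | 380-463 | 84 |
| | Week 72 (463, 547] | 464-547 | 84 |
| | Week 84 (547, 631] | 548-631 | 84 |
| | Week 96 (631, 687] | 632-687 | 56 |
| | **Total** | 352-687 | **336** |
| ECG | Week 48 (253, 505] | 352-505 | 154 |
| | Week 96 (505, 687] | 506-687 | 182 |
| | **Total** | 352-687 | **336** |
| Coagulation | Week 48 [1, 505] | 352-505 | 154 |
| | Week 96 (505, 687] | 506-687 | 182 |
| | **Total** | 352-687 | **336** |

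As a share of the Part B windowed period: 336 / 687 = 48.9%. With a cut-off of 687 in Part B, the overlap is 0 for every assessment.

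**Is 687 the Part B counterpart of 351?** Dosing in Part A runs "Day 1 through evening before Part A Week 48 Visit" and in Part B "Day 1 through evening before Part B Week 96 Visit". The nominal last dose is therefore day 336 or day 672. Safety Follow-up at 28 ± 7 days falls on days 357-371 (336 + 21 to 336 + 35) or 693-707 (672 + 21 to 672 + 35). The gap from cut-off to the opening of follow-up is 357 − 351 = 6 days in Part A and 693 − 687 = 6 days in Part B. So 687 does in Part B what 351 does in Part A.

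**Examples, Part B, no nominal Safety Follow-up visit.**

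- ETT visits on days 351 and 352 share the Week 48 window for every assessment above. Day 351 goes to Week 48 and day 352 to Safety Follow-up.
- An ETT visit on day 421 is on the exact Week 60 target (7 × 60 + 1) and goes to Safety Follow-up.

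**Scope.** Weight and height share the Panel B windows, but the "Height and weight" row of Protocol Table 3-2 has no entry at the ETT visit, so they are unaffected as scheduled. Departures to another qualified study are uncertain. Section 9.1.2 lists them among the transitions, but Section 9.1.3 gives them a Departing Visit, says of those who do not return that "they will not be required to complete a separate ETT visit", and reserves ETT for stopping treatment "for any reason other than to enroll in another qualified Vertex study, an ETT Visit should be scheduled as soon as possible". They count only if the Departing Visit is coded as ETT.

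**The case against.** Three points deserve weight.

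First, the footnote does not say that the ETT value leaves its week window. Since footnote 2 applies the windows to all visits, the value could fill both rows. That is so, and the consequence depends on reading the mapping as one analysis visit per ETT visit. This is the natural reading. The alternative reports one measurement in two rows, and then footnotes 2 and 4 need to be reconciled anyway.

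Second, in the routes the protocol describes, the ETT visit replaces Safety Follow-up, so the follow-up label is not absurd. This stands in part, most clearly for visits 3 weeks or more after the last dose. But footnote 4 tests study day, not time since dose or replacement status. It separates days 351 and 352 for no protocol reason. It also catches a subject who attends an ETT visit and then misses a required Safety Follow-up visit.

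Third, the 336 days describe the rule and not the data. That is correct. At most one ETT visit per affected subject moves, and only where the nominal follow-up visit is absent. SAP Section 9.2.1 also allows Part B not to be summarised if few subjects roll over, although it regards that as unlikely.

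**Conclusion.** The footnote is wrong as written, at minor severity. Its cut-off is the end of the last Part A window and has no meaning in Part B, where it overlaps the week windows on 336 study days (352-687), against 0 in Part A. The arithmetic is certain. That a value is lost from its week row assumes the footnote overrides the windows.

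The effect is confined to the Part B descriptive by-visit summaries of vital signs, hematology, chemistry, ECG and coagulation. Adverse event tables, threshold counts over the treatment-emergent period and listings are unchanged, and no hypothesis is tested. The number of subjects affected cannot be worked out from the documents.

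**What to change.** In footnote 4, replace the single cut-off with *study day >351 in Part A or >687 in Part B*, and add: *ETT visits on or before those days follow the Table 12-1 windows.*

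One small downside: Part B ETT visits on days 352-687 that come 3 weeks or more after the last dose would then sit in week rows, as Part A visits up to day 351 already do. If the sponsor prefers to keep these as follow-up, add an OR condition for ETT visits that replace Safety Follow-up under Protocol Section 9.1.3, and exempt them from the added sentence. The sponsor should then also say whether the condition extends to the transition visits in Section 9.1.2, and apply the same condition in both parts.

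The cost is one SAP footnote, with no new data.

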			
2. Age (in months) at first dose date and post-baseline visit (for use in calculation of Height, BMI and weight z-scores):
 
Obtain the age at informed consent in “yy, mm” format (e.g., 24 years, 6 months) in parent study from the VS page at the Screening Visit in the parent study.
 
Obtain the informed consent date in parent study.
 
Then age (in months) at first dose or post-baseline visit = integer part of {(age at informed consent (in months) in parent study + 0.5 + diff(first dose date or post-baseline visit date, informed consent date) in months in parent study)} + 0.5.

			
3. Missing first dose date or last dose date
 
If the first dose date is missing, use Day 1 visit date.
 
If the last dose date of study drug is not available and there is no data to indicate that the subject discontinued treatment, the data cutoff date will be used instead.
 
If the subject discontinued treatment and the last dose date is missing or partial date is reported, the last dose date will be imputed based on, in descending order priority, the Early Treatment Termination (ETT) visit date, last visit date before the Safety Follow-up, or the last study drug administration date from EX SDTM domain, as appropriate. The imputation algorithm will ensure the imputed last dose date does not exceed the study participation end date.

			
4. Electrocardiogram:
 
Baseline is defined in Section 9.1.1 for Part A and 9.2.1 for Part B. If multiple ECG measurements are obtained on the same calendar day during the TE period,
 
 ○ For summary purpose, the average value will be used as the ECG on that day; ○ For threshold analysis purpose, all ECG values will be used

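### For discontinued subjects, a missing or partial last-dose date is imputed from the ETT visit before the dosing record, without respecting a known month, so exposure is overstated

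*SAP*

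**What the plan says.** SAP 12.1, Derived Variables item 3, has two separate branches for the last-dose date.

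- **Discontinued subjects.** "If the subject discontinued treatment and the last dose date is missing or partial date is reported", the date is imputed "in descending order priority, the Early Treatment Termination (ETT) visit date", then the last visit before Safety Follow-up, "or the last study drug administration date from EX SDTM domain, as appropriate". A cap follows: "The imputation algorithm will ensure the imputed last dose date does not exceed the study participation end date".
- **Subjects not known to have discontinued.** If the last-dose date is unavailable and "there is no data to indicate that the subject discontinued treatment, the data cutoff date will be used instead".

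Protocol 9.1.3 has the ETT Visit arranged promptly once the decision to stop is made, but sets no limit in days. "If the ETT Visit occurs 3 weeks or later following the last dose of study drug", it replaces the Safety Follow-up Visit, and under Protocol 9.1.5 it then becomes the date of completion of participation. For completers, Protocol Table 3-1 states: "The last dose of Part A should be taken on the evening before the Week 48 Visit". Table 3-2 likewise ends Part B dosing on the evening before Week 96.

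SAP 9.1.2.5 defines exposure as last dose minus first dose plus 1 day, within the TE Period. SAP 9.1.2.6 divides by that duration to obtain compliance, which is then cut at 80%. SAP 9.1.3.1 and 9.1.3.10 present exposure-adjusted rates without defining their denominator. SAP 9.2.1 uses the same exposure and compliance definitions for Part B.

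**The concern.** The one source in the list that records dosing is ranked below two visit dates. An ETT date is normally later than the last dose. Under Protocol 9.8.1, for example, drug is interrupted for marked transaminase elevation before confirmatory testing, and permanent discontinuation is decided afterwards. The last dose can therefore precede even the decision to stop, in subjects with an adverse event of special interest.

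The rule also applies when a partial date was reported, and it can override what is known. A last dose recorded only as March becomes an April date if the ETT Visit was in April. This is out of line with SAP 12.2 and 12.3, where partial medication dates and adverse-event start dates are generally completed from the known month or year.

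At stake are exposure duration, the compliance percentage and its 80% category, and possibly the exposure-adjusted rates. If those rates use exposure duration as their denominator, false days of exposure make the drug look safer.

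**Working it through.** The plan states no figure to reproduce, because the study is descriptive. The check is date arithmetic on the plan's definitions.

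**Inputs.** Let the true last dose be day 0 and g the days from it to the ETT Visit. The TE Period ends at min(last dose + 28, completion of participation) (SAP 9.1.1). Safety Follow-up falls on days 21 to 35 (28 ± 7, Protocol 9.1.2). If g is 21 or more, ETT replaces it and is the completion date. Part A lasts 48 × 7 = 336 days, and about 158 subjects are expected. The documents give neither g nor the number of affected subjects, so both are assumed ranges.

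**Exposure.** The error is +g days. The participation-end cap does not reduce it: when ETT replaces Safety Follow-up, the cap is the ETT date itself. With g = 21:

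| True exposure | Overstatement | Rate multiplier, if exposure is the denominator |
|---|---|---|
| 28 days | 21/28 = 75% | 28/49 = 0.57 |
| 84 days | 21/84 = 25% | 84/105 = 0.80 |
| 168 days | 21/168 = 12.5% | 168/189 = 0.89 |

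**Compliance.** Assume 14 interruption days in 56, with the added days not counted as interruption. The true value is 100 × (1 − 14/56) = 75.0%. With 21 false days it is 100 × (1 − 14/77) = 81.8%, which crosses the 80% cut.

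**Pooled Part A person-time.** If all subjects complete, the total is 158 × 336 = 53,088 days. With g = 21:

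- 3 affected: 63/53,088 = 0.12%
- 8 affected: 168/53,088 = 0.32%
- 16 affected: 336/53,088 = 0.63%

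For 3 to 16 affected subjects, g = 7 gives 0.04% to 0.21% and g = 35 gives 0.20% to 1.05%.

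**TE Period.**

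| Gap g | Completion | True TE end | TE end with imputed date | Added days |
|---|---|---|---|---|
| under 21 | Safety Follow-up, day 21 to 28 | that visit | that visit | 0 |
| 7 to 20 | Safety Follow-up, day 35 | 28 | 35 | 7 |
| 21 | ETT, day 21 | min(28, 21) = 21 | min(49, 21) = 21 | 0 |
| 28 | ETT, day 28 | 28 | 28 | 0 |
| 35 | ETT, day 35 | 28 | 35 | 7 |
| 42 | ETT, day 42 | 28 | 42 | 14 |

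Beyond 28 days the stretch is g − 28. With an on-window Safety Follow-up it is at most 7 days.

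**Cutoff branch.** A completer did not discontinue, so a completer with a missing last-dose date falls here as the text stands. The SAP covers final analyses (section 4), plans no interim (10.1) and does not define the cutoff date. The cap is stated only in the discontinued-subject paragraph. Because exposure is taken within the TE Period, which ends no later than completion, the excess in Part A is 1 day when the Week 48 Visit is the completion date. It is up to 35 days (35/336 = 10.4%) when Safety Follow-up is.

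**The case against.** The strongest counter-argument concerns the remedy. The rule operates only when the last-dose date is missing or partial, and the documents do not describe what EX then holds. If EX holds only a last known record, it is a lower bound. Ranking it first without condition could understate exposure and close the TE Period early, moving events out of tables that show TEAEs only. This stands, and the fix has to allow for it. It is also fair that ETT is meant to be prompt, that the ranking carries the qualifier as appropriate, and that results are pooled and descriptive. These limit the size of the problem. They do not explain why a known month and year may be overridden, and the qualifier does not say when EX should take precedence.

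Three stronger readings are tempting, and the documents do not support them.

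- **That the TE Period is stretched in general.** The completion-date limit makes the stretch zero in most cases, including a 21-day gap.
- **That the data cutoff outranks the dosing record.** It is a separate branch for subjects with no sign of discontinuation and is not part of the ranking.
- **That a Part A completer continuing in Part B could gain Part A exposure as long as Part B itself.** Protocol 9.1.2 and 9.1.5 make the Week 48 Visit the completion date for a subject moving to Part B within 28 days of the last dose. SAP 9.1.1 and 9.1.2.5 then hold Part A exposure at about that visit.

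**Conclusion.** The concern holds for exposure and compliance in discontinued subjects. The stated order favours a date that normally follows the last dose, and the rule can contradict a reported month. For an affected early discontinuer the distortion can be large. For the pooled results it is small, and under 1% of Part A person-time across most of the assumed ranges. Any effect on exposure-adjusted rates depends on the undefined denominator being exposure duration.

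Misclassification between treatment-emergent and post-treatment events is a minor issue. It arises mainly when ETT falls more than 28 days after last dose. The 7-day limit for shorter gaps assumes that Safety Follow-up took place within its window. The cutoff branch needs tidying for completers but is not a source of large error.

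**What to change.** Revise item 3 of SAP 12.1 for both parts:

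1. Keep the imputed date within any reported month and year, and use the ETT date or last on-treatment visit as an upper bound.
2. Use a complete EX last-administration date ahead of ETT when it is a recorded stop. Otherwise treat it as a lower bound.
3. For a subject who completed a part and has no last-dose date, impute the day before the Week 48 or Week 96 Visit instead of the data cutoff. Apply the participation-end cap to both branches.
4. Report the number of imputed last-dose dates.

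The cost is one SAP paragraph and a small programming change, with no new data. The downside is that exposure may be slightly understated, and the TE Period slightly shorter, for the few affected subjects. The count in step 4 lets a reader judge whether this matters.
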